2.2.3.3 Endoscopic Change Variables

- Change from baseline to week 26 in Crohn's Disease Endoscopic Index of Severity (CDEIS) and Simple Endoscopic Score for Crohn's Disease (SES-CD). The CDEIS and SES-CD are endoscopic scoring systems for the assessment of CD.
- Correlations between the change from baseline to week 26 in CDEIS and SES-CD and the change from baseline to week 26 in CDAI.
- Proportion of subjects in remission by visit time post-baseline based on CDEIS and SES-CD measurements. Remission is defined as 0-3 score based on CDEIS measurement and defined as 0-2 score based on SES-CD measurement.
- Proportion responders based on CDEIS and SEC-CD at week 26. Responders based on CDEIS and SES-CD scores are defined and classified into two categories as 50% reduction from baseline score; and 25% reduction from baseline score to week 26.

2.2.3.4 Health Related Quality of Life Variables

- Change from baseline in the Short Form-36 Health Survey (SF-36) domain and component scores at each follow-up visit time point.

- Change from baseline in the IBDQ score at each follow-up visit time point. Inflammatory Bowel Disease Questionnaire (IBDQ) score is designed to measure effects of subject's inflammatory bowel disease on their daily functions and quality of life during last 2 weeks.

2.2.3.5 Markers of Inflammation Variables

Inflammation parameters include the following:

- Change from baseline in C-reactive protein
- Change from baseline in Fecal calprotectin

2.2.4 Other Exploratory Efficacy Endpoints/Variable(s)

2.2.4.1 Map Detection Endpoints/Variable

As specified in the objectives, the variables/endpoints in this section are intended to be for exploratory analysis. Depending on the availability of data, specific details of additional exploratory analyses to be conducted will be determined at the time of analyses.

Mycobacterium avium subsp. paratuberculosis (MAP) detection parameters include the following:

- Proportion of subjects with a MAP positive PCR blood assay at baseline.
- Proportion of subjects with a change in MAP blood PCR assay status after week 26 and after week 52 of treatment compared to baseline.
- Proportion of subjects with a MAP positive blood culture at baseline.
- Proportion of subjects with a change in MAP blood culture status after 26 weeks of treatment compared to baseline.
- Proportion of subjects with a change in MAP blood culture status after 52 weeks of treatment compared to baseline.
- Proportion of subjects with MAP positive colon biopsy PCR assay at baseline.
- Proportion of subjects with a change in MAP positive colon biopsy PCR assay status after 26 weeks of treatment compared to baseline.
- Proportion of subjects with a change in MAP positive colon biopsy PCR assay status after 52 weeks

2.2.4.2 Other Endpoints

- Proportion of subjects tapered off steroids in each treatment arm.
- Assess tissue levels of the active agents of RHB-104 in colon biopsy samples if possible.

2.2.5 Safety Endpoints/Variables

Safety parameters include the following.

- Adverse events
- Incidence of uveitis
- Laboratory parameters (hematology, chemistry, urinalysis)
- Vital signs
- ECG
- Physical examination
- Concomitant medications

3. STUDY DESIGN

This study is a multicenter, Phase III, randomized, placebo-controlled, parallel group, double-blind study designed to evaluate the efficacy and safety of RHB-104 compared to placebo to treat subjects with moderate to severe CD. RHB-104 consists of 3 antibiotics with activity against *Mycobacterium avium subsp. paratuberculosis* (MAP), a potential cause of CD. Subjects with active CD will be randomized at baseline in a 1:1 fashion to receive up to 52 weeks of RHB-104 or placebo. Subjects will remain on stable doses of their baseline CD treatment although steroids may be tapered after Week 8 at the discretion of the investigator.

The study is designed to assess remission at Week 26 as the primary endpoint. However, as MAP are slow growing mycobacteria without a proven antibiotic treatment, the duration of antibiotic treatment needed to achieve remission in subjects with CD caused by MAP may be longer than 26 weeks. Subjects with response at week 26 may ultimately achieve remission at a later time point with continued treatment for MAP. Also, subjects with CD treated for underlying MAP infection may experience benefits with a longer period of time in response or remission with RHB-104 treatment compared to placebo. Thus, the study is also designed to assess response, remission, and maintenance of remission in subjects on randomized treatment through week 52.

Blood samples will be collected at baseline and at every visit after the initial 4 weeks of treatment to test for MAP in the serum using a polymerase chain reaction (PCR) assay. MAP cultures will be prepared from whole blood at the baseline visit and after 26 and 52 weeks of treatment in subjects enrolled at North American study sites.

Safety and pharmacokinetics of the fixed-dose combination product, RHB-104, will also be assessed. Colonoscopy will be done in consenting subjects prior to initiation of study drug and after 26 weeks of study drug to assess for mucosal healing as well as MAP status via PCR and culture. Optional biopsies will also be collected for possible measurement of tissue drug levels and archived for future MAP determinations.

4. SCHEDULE OF ASSESSMENTS AND TREATMENT ASSIGNMENT

4.1 Schedule of Assessments

The study schedule is summarized in the study visit schedule table below.

4.1.1 Study Visit Schedule

	Screening (Day -42 to screening Day -7)	Baseline Day 1 / Week 0 ⁶	Week 2	Week 4	Week 6	Weeks 8, 12, 16 and 20	Week 26	Weeks 35 and 44	Week 52	Week 56
Study Visit Window			± 3 days	± 3 days	± 3 days	± 7 days	± 7 days	± 7 days	± 7 days	± 7 days
Informed Consent	X									
Inclusion/ Exclusion Criteria Demography and Medical History	X	X								
Concomitant Medications Assessment	X	X	X	X	X	X	X	X	X	X
Vital Signs and Physical Examination	X	X	X	X	X	X	X	X	X	X
Adverse Event Assessments			X	X	X	X	X	X	X	X
CDAI collection ¹		X		X		X	X	X	X	
Subject Assessments: IBDQ and SF-36		X					X		X	
Uveitis Assessment	X	X	X	X	X	X	X	X	X	X
ECG ²	X	X	X	X		Weeks 8 and 12	X		X	
Hematology and Biochemistry	X	X	X	X	X	X	X	X	X	X
Urinalysis ³	X	X	X	X	X	X	X	X	X	X
Plasma Levels of RHB-104 ⁴							X			
Hep B S Ag, Hep C Ab, HIV and QuantiFERON®-TB	X									
C-Reactive Protein (CRP)	X	X				X	X	X	X	
MAP Testing Blood with Additional Sample for Future Use		X		X		X	X	X	X	
MAP culture from blood		X					X		X	
Fecal calprotectin	X	X				Week 12	X		X	
Stool Testing other ⁵	X						X		X	
Pregnancy Test Urine	X	X	X	X	X	X	X	X	X	X
Colonoscopy ⁶ and CDEIS, storage of images, MAP testing , archive samples and possible analysis of drug levels		X					X			
Population PK Blood Sampling ⁴			X	X	X	Week 8, 12 and 20		X	X	X ⁸
Randomization (after meeting inclusion/exclusion criteria) ⁷		X								

Study Drug and Diary Dispensing (with instructions for drug administration & diary completion ¹)	Diary only	X	X	X	X	X	X	X		
Drug Return & Accountability			X	X	X	X	X	X	X	
Telephone reminder of dose escalation		Day 7	Day 21							

¹ **CDAI:** Subjects will complete a CDAI diary for the 7 days preceding their next study visit. To ensure compliance, site personnel will contact subjects prior to initiation of the CDAI-recording period, to review the process for adequate CDAI data collection. At the screening visit the 7-Day CDAI diary will be distributed to the subject for completion before the Baseline visit and if applicable, before the colonoscopy preparation/procedure takes place.

² **ECG:** Five minute continuous digital 12-lead ECG after resting 10 minutes in a supine position

³ **Urine Testing:** Dipstick test only, unless results are abnormal

⁴ **Frozen plasma sample:** For Week 26 clarithromycin, rifabutin, clofazimine, 14-hydroxy-clarithromycin, and 25-O-desacetyl-rifabutin plasma concentration measurement.

⁵ **Stool testing:** *E. coli* 0157 toxin, culture (includes *salmonella*, *campylobacter*, *yersinia*), ova, and parasites testing done at Screening only. *C. difficile* toxin and stored sample for potential analysis of fecal microbiome done at Screening, Weeks 26 and 52

⁶ **Colonoscopy:** to be performed at least 8 days before or at the Week 0 visit. If performed at the Week 0 visit, then the 7 days prior to the start of the colonoscopy preparation will be used to calculate the baseline CDAI score. At visit week 26: the colonoscopy must be performed 3-4 days post visit week 26. Only CDEIS compatible colonoscopies will have biopsies and CDEIS performed, although biopsies are optional.

⁷ **Randomization:** At screening, IWRS will be accessed to record the subject’s screening information. Randomization and study drug kit assignment will be confirmed in the IWRS at the baseline visit, after subject eligibility is confirmed.

⁸ **PK Blood Sampling:** single time point.

4.2 Dosage and Administration of Study Drug

Study treatment will be taken twice-daily (bid) with food. Subjects will self-administer study drug orally, as per the following dosage schedule:

		Weeks				
		1	2	3	4	5-52
		(1 bid) 2 capsules	(2 bid) 4 capsules	(3 bid) 6 capsules	(4 bid) 8 capsules	(5 bid) 10 capsules
		Active Daily Dose (mg)				
Active Treatment Arm	RHB-104	190mg	380mg	570mg	760mg	950mg
	Clarithromycin	90mg	180mg	270mg	360mg	450mg
	Rifabutin	20mg	40mg	60mg	80mg	100mg
Placebo Arm	Clofazimine	placebo	placebo	placebo	placebo	placebo
	Placebo	placebo	placebo	placebo	placebo	placebo

4.3 Randomization and Treatment Assignment Procedures

A total of 410 subjects that meet study eligibility requirements will be randomly assigned in permuted blocks to receive active (RHB-104) or placebo treatment in a 1:1 ratio using an Interactive Web Randomization System (IWRS). Randomization will be performed within strata defined by whether subjects use protocol permitted anti-TNF agents (yes/no). The randomization

code will only be available to personnel responsible for the randomization of subjects or labeling of the study drug. The sponsor and all personnel involved in the conduct of the study will be blinded to the treatment assigned to each subject.

5. ANALYSIS POPULATIONS

All screened subjects who signed informed consent will be included in the disposition table counts.

The following populations will be used for data analysis.

The Intent-to-Treat (ITT) Population: The primary efficacy analyses will be based on the ITT population, which is defined as all subjects randomized. Subjects will be analyzed according to the treatment group to which they were randomized.

The Modified Intent-to-Treat (mITT) Population: The Modified Intent-to-treat population is defined as patients who fulfill all inclusion/exclusion criteria. The sensitivity analyses will be performed using the mITT population. Subjects will be analyzed according to the treatment group to which they were randomized.

The Safety Population (SAF): The safety population includes subjects who are randomized and receive at least one dose of study medication. The primary safety analyses will be based on the SAF population. Subjects will be analyzed according to the treatment which they actually received.

Per-Protocol Population (PP): The PP Population includes all randomized subjects who receive at least one dose of RHB-104 or placebo and complete dose escalation to target dose of 5 capsules bid, as well as all subjects without major protocol deviations that would have a significant impact on clinical outcome. Relevant protocol deviations may include errors in treatment assignment, the use of excluded medication that might affect study drug bioavailability, poor compliance (< 80% compliant over study duration), and subjects lost to follow-up. Protocol deviations will be reviewed and the list of major deviations warranting exclusion from the PP Population will be finalized prior to study unblinding. Subjects will be analyzed according to the treatment group to which they were randomized.

The primary and key secondary efficacy sensitivity analyses may be repeated on the PP Population.

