	The study is designed to assess remission at Week 26 as the primary endpoint. However, as MAP are slow growing mycobacteria without a proven antibiotic treatment, the duration of antibiotic treatment needed to achieve remission in subjects with CD caused by MAP may be longer than 26 weeks. Subjects with response at week 26 may ultimately achieve remission at a later time point with continued treatment for MAP. Also, subjects with CD treated for underlying MAP infection may experience benefits with a longer period of time in response or remission with RHB-104 treatment compared to placebo. Thus, the study is also designed to assess response, remission, and maintenance of remission in subjects on randomized treatment through week 52.				

	Blood samples will be collected at baseline and at every visit after the initial 4 weeks of treatment to test for MAP in the serum using a polymerase chain reaction (PCR) assay MAP cultures will be prepared from whole blood collected at the baseline visit and after 26 and 52 weeks of treatment.						
	Safety and pharmacokinetics of the fixed-dose combination product, RHB-104, will also be assessed.						
	Colonoscopy will be done in consenting subjects prior to initiation of study drug and after 26 weeks of study drug to assess for mucosal healing as well as MAP status via PCR and culture. Optional biopsies will also be collected for possible measurement of tissue drug levels and archived for future MAP determinations.						
	Study Visit Schedule:						
	Screening, baseline, and follow-up visits at weeks 2, 4, 6 (+/- 3 days), 8, 12, 16, 20, 26, 35, 44, 52, and 56 (+/- 7 days). Subjects undergoing colonoscopy will have a procedural visit after week 26 assessment so as to not interfere with data collection.						
Subject Participation Duration:	Subjects are expected to participate up to 62 weeks. However, subjects who complete 26 weeks of study drug administration and remain out of remission e.g. CDAI ≥150, will be eligible for open label treatment with RHB-104 in an extension study (protocol RHB-104-04). Subjects may elect to continue in the RHB-104-01 study, and will remain in the RHB-104-01 study until study drug administration in the RHB-104-04, if applicable.						
Treatment:	RHB-104; a fixed-dose combination of 95 mg clarithromycin, 45 mg rifabutin, and 10 mg clofazimine. Placebo is a capsule with a similar appearance as RHB-104.						
Route of Administration:	Oral capsule.						

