6.2.4.2 Accountability/Compliance

Drug compliance will depend upon capsule counts at each visit. Subjects are instructed to bring their study medication and all empty packages to each clinic visit. Compliance will be assessed by capsule counts recorded by each site for each subject. The details of medication used will be recorded and reconciled against expected medication use. Compliance will be calculated as the reported medication used by subject as percentage (%) of expected usage. Summary descriptive statistics will be presented for the number and proportion of subjects non-compliant (< 80% compliant) for safety population.

Extent of compliance of each subject data will be presented in subject listing for the SAF population.

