8.1 Tables, Listings and Graphs (TLFs) for Study Report

List of Tables and Graphs:

Table Number	Title
Analysis Populations and Disposition	
Table 14.1.1.1	Subject Disposition: All Enrolled Subjects
Table 14.1.1.2	Major Protocol Deviations: Intent-to-Treat Population
Table 14.1.1.3	Major Protocol Deviations: Safety Population (if different from ITT)
Demographics and Baseline Characteristics	
Table 14.1.2.1	Demographics and Baseline Characteristics: Intent-to-Treat Population
Table 14.1.2.2	Demographics and Baseline Characteristics: Safety Population (if different from ITT)
Table 14.1.2.3	Vital Signs at Baseline: Intent-to-Treat Population
Table 14.1.2.4	Physical Examination at Baseline: Intent-to-Treat Population
Medical History	
Table 14.1.3.1	Crohn's Disease History: Intent-to-Treat Population
Table 14.1.3.2	Crohn's Disease Prior Treatments: Intent-to-Treat Population
Prior and Concomitant Medications	
Table 14.1.4.1	Prior Medications Use: Intent-to-Treat Population
Table 14.1.4.2	Concomitant Medications Use: Intent-to-Treat Population
Table 14.1.4.3	Prior anti-TNF Agents Use: Intent-to-Treat Population
Table 14.1.4.4	Crohn's Disease Concomitant Medications Use: Intent-to-Treat Population
Table 14.1.4.5	Prior Steroids Use: Intent-to-Treat Population
Table 14.1.4.6	Concomitant Steroids Use: Intent-to-Treat Population
Table 14.1.4.7	Crohn's Disease Concomitant Steroids Use: Intent-to-Treat Population
Table 14.1.4.8	Prior Immunomodulators Use: Intent-to-Treat Population
Table 14.1.4.9	Concomitant Immunomodulators Use: Intent-to-Treat Population
Treatment Exposure and Compliance	
Table 14.1.5.1	Study Drug Exposure: Intent-to-Treat Population
Table 14.1.5.2	Treatment Compliance: Intent-to-Treat Population
Primary Efficacy Endpoint	
Table 14.2.1.1	Primary Objective – Remission Week 26: Intent-to-Treat Population

Table 14.2.1.2	Sensitivity Analysis: Remission Week 26: Modified intent-to-Treat Population
Table 14.2.1.3	Sensitivity Analysis: Remission Week 26: Per-protocol Population
Table 14.2.1.4	Sensitivity Analysis: Remission Week 26: Completers Analysis (Observed Cases)
Table 14.2.1.5	Exploratory: Remission Week 26 by Treatment Group for Each Baseline Subgroup from Logistic Regression analysis: Intent-to-Treat Population
Figure 14.2.1.1	Exploratory: Remission Week 26 Forest Plots by Treatment Group for Each Baseline Subgroup Analysis: Intent-to-Treat Population
Key Secondary Efficacy Endpoints	

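### The single per-protocol set has no cut-off at the endpoint visit, so capsule-taking or loss after Week 26 can decide who is in the Week 26 and Week 16 per-protocol analyses

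*SAP*

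**What the plan says.** SAP section 5 defines one Per-Protocol (PP) population for all efficacy endpoints. Beyond at least one dose and completed dose escalation, membership depends on having no major deviation. The deviations are given as examples: "Relevant protocol deviations may include errors in treatment assignment", then certain excluded medication, "poor compliance (< 80% compliant over study duration", and loss to follow-up. Neither of the last two is tied to an endpoint visit. The section adds that "the list of major deviations warranting exclusion from the PP Population will be finalized prior to study unblinding" and that "The primary and key secondary efficacy sensitivity analyses may be repeated on the PP Population".

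SAP section 6.2.4.2 gives the compliance formula: "Compliance will be calculated as the reported medication used by subject as percentage (%) of expected usage". It does not say whether expected usage stops when a subject leaves or runs to the end of the planned course. Under SAP section 3, subjects are "randomized at baseline in a 1:1 fashion to receive up to 52 weeks of RHB-104 or placebo".

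SAP section 8.1 lists the table "Sensitivity Analysis: Remission Week 26: Per-protocol Population" and matching PP tables for all five key secondary endpoints, which are assessed at Week 16, at Week 26, at Week 52 and from Week 26 through Week 52.

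The protocol synopsis, under Subject Participation Duration, says that "subjects who complete 26 weeks of study drug administration and remain out of remission e.g. CDAI ≥150, will be eligible for open label treatment" in study RHB-104-04. The move is elective, and such subjects may stay in this trial.

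**The concern.** A PP analysis of a Week 26 endpoint should describe subjects who followed the protocol up to Week 26. Capsules taken or missed later cannot change a Week 26 outcome. A compliance figure taken over the whole study lets them change who is analysed, and subjects lost after Week 26 can be removed although their endpoint was observed. The same holds, over a longer later period, for Week 16 remission.

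There is a second, conditional worry. Non-remission at Week 26 opens the route to open-label treatment. If leaving by that route lowered the compliance score, subjects would be removed because of the outcome being analysed, and the PP remission rates would be conditioned on remission itself.

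**Working it through.** **The plan's own figures.** The documents give no figure for the PP set. The design rates used below (36% RHB-104, 21% placebo; protocol Statistical Considerations and SAP 6.1.9) do fit the stated sample sizes. At 90% power and two-sided alpha 0.05, a continuity-corrected two-proportion calculation gives 202 per arm, 404 in all, close to the stated 410. At 162 per arm and alpha 0.049, power is 85.0% uncorrected and about 82% corrected, in line with the stated 80% or more.

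**Scheduled capsules** (SAP 4.2: 2, 4, 6 and 8 a day in Weeks 1 to 4, then 10 a day).
- Weeks 1 to 4: 7 × (2 + 4 + 6 + 8) = 140
- To Week 16: 140 + 12 × 70 = 980
- To Week 26: 140 + 22 × 70 = 1,680
- To Week 52: 140 + 48 × 70 = 3,500
- 80% threshold over 52 weeks: 0.80 × 3,500 = 2,800

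**Step 1: subjects treated to Week 52.** For them, planned course and time on drug coincide, so the result does not depend on how expected usage is read.
- Full compliance to Week 26: the later compliance needed to stay in is (2,800 − 1,680) / (3,500 − 1,680) = 1,120 / 1,820 = 61.5%. Anything lower removes the subject.
- Full compliance after Week 26: the Week 26 compliance needed to stay in is (2,800 − 1,820) / 1,680 = 980 / 1,680 = 58.3%. Such a subject is kept, although well under 80% during the endpoint period.
- Week 16 endpoint, same method: the corresponding limits are (2,800 − 980) / 2,520 = 72.2% after Week 16 and (2,800 − 2,520) / 980 = 28.6% before it.

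**Step 2: a fully compliant subject who leaves at Week 26.**
- Expected usage is the planned 52 weeks: 1,680 / 3,500 = 48%, below threshold. A perfect taker reaches 80% only at Week 42, since (2,800 − 140) / 70 + 4 = 42.
- Expected usage stops at last dose or at Week 26: 1,680 / 1,680 = 100%, kept.

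**Step 3: size under the 52-week reading only.** Let p be the true remission rate and f the share of Week 26 non-remitters who roll over and are excluded. Assume that every remitter is kept. The PP rate is p / [p + (1 − p)(1 − f)]. The documents give no value for f, so a range is shown, equal in both arms:

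| f | RHB-104 | Placebo | Difference (points) |
|---|---|---|---|
| 0 | 36.0% | 21.0% | 15.0 |
| 0.25 | 42.9% | 26.2% | 16.7 |
| 0.50 | 52.9% | 34.7% | 18.2 |
| 0.75 | 69.2% | 51.5% | 17.7 |
| 0.90 | 84.9% | 72.7% | 12.2 |

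The odds are p / [(1 − p)(1 − f)], so a common f cancels from the odds ratio, which stays at 2.12. With equal true rates and equal f there is no difference to find.

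Unequal f behaves differently. With 21% true remission in both arms and f = 0.6 on RHB-104 and 0.4 on placebo, the rates are 0.21 / (0.21 + 0.79 × 0.4) = 39.9% and 0.21 / (0.21 + 0.79 × 0.6) = 30.7%. That is +9.2 points, odds ratio 1.50. Swapping the shares gives −9.2 points, odds ratio 0.67. For scale, the plan calls 9 points clinically meaningful.

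**The case against.** The PP analysis carries little weight. The primary test is on the ITT population with missing Week 26 assessments counted as non-remission, the gatekeeping sequence in SAP 6.1.2 uses no PP result, and the firm commitment to robustness analyses in SAP 6.3.1 names the mITT and observed-case sets, with PP only as something that may be done. The deviations are examples, exclusion requires a significant impact on clinical outcome, and the list is settled before unblinding, so a careful review could keep a subject whose only lapse came after Week 26. All of this stands and limits the consequence. It does not remove the gap: 80% over the study is the only compliance threshold offered for PP, nothing tells the reviewers to disregard later events, and blinding conceals treatment but not CDAI results or rollover.

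A reader might infer that moving to open-label treatment in itself removes Week 26 non-remitters from the PP set. The documents do not support that. The SAP does not equate study duration with 52 weeks for every subject, treatment lasts up to 52 weeks, and SAP 6.2.4.1 ends time on treatment at the last dose. If expected usage ends there too, the leaver scores 100%. A transfer that the protocol permits is also neither an obvious major deviation nor, in ordinary terms, loss to follow-up.

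**Conclusion.** The point holds as a minor one. The PP definition, followed as written, can remove subjects who adhered throughout the endpoint period and keep subjects who did not. The 61.5% and 58.3% limits rest only on the capsule schedule, the 80% threshold and treatment to Week 52.

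Selection on the outcome through rollover is a possibility left open by the undefined expected usage, not an established feature of the plan. Its size depends on the 52-week denominator, an assumed rollover share, exclusion of all who roll over and retention of all remitters. A reader might also conclude that the PP analysis would falsely favour RHB-104. Equal rollover does not show this, because it creates no difference under the null. Unequal rollover could push the result either way, and the documents give no basis for expecting one direction.

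**What to change.** Before unblinding, amend SAP sections 5 and 6.2.4.2 as follows:
- Assess compliance and loss to follow-up from first dose up to the visit of the endpoint analysed (Week 16, 26 or 52), with a PP set for each time point.
- Define expected usage as the capsules scheduled over that same window.
- State that moving to RHB-104-04 after the Week 26 visit does not exclude a subject from the Week 16 or Week 26 PP sets.

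This also gives every subject the same window for a given endpoint. That would matter if the data were cut when about 324 subjects have completed Week 26, the trigger for the final analysis in SAP 6.1.9, because some subjects would then have no later counts.

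The cost is a few lines of SAP text and one PP flag per endpoint time. The capsule counts are already taken at each visit, so no new data are needed.
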